#### 10.1.1.3 Severity Assessment

Severity assessments are based on the intensity of the event in relation to expectation. The investigator will assess the intensity of AEs based on the following definitions:

- Mild (awareness of sign or symptom, but easily tolerated)
- Moderate (discomfort sufficient to cause interference with normal activities)
- Severe (incapacitating, with inability to perform normal activities)

Severity is a measure of intensity where seriousness is defined by the criteria outlined in [Section 10.1.1.2](#). An AE of severe intensity need not necessarily be considered serious. For example, nausea that persists for several hours may be considered severe nausea, but not meet serious criteria, and therefore would be assessed as a severe AE but not an SAE.

#### 10.1.1.4 Causality Assessment

The investigator determines the causality of all AEs to the study drug using medical judgment and considering all relevant factors such as (but not limited to) the underlying study indication, coexisting disease, concomitant medication, relevant history, pattern of the AE, temporal relationship to the study drug, and de-challenge or re-challenge. The causality assessment of the AE/SAE is to be made as follows.

### **Related to study drug (possibly, probably, or definitely related)**

Based on medical judgment, there is at least a reasonable possibility that the study drug caused the event; one or more of the following criteria apply:

- The event follows a reasonable temporal sequence from administration of study drug
- The event could not be reasonably attributed to the known characteristics of the patient's clinical state, environmental or toxic factors, or other modes of therapy administered to the patient
- The event follows a known pattern of response to study drug
- The event disappears or decreases on cessation or reduction in dose of the study drug. (It should be noted that in some situations an AE will not disappear or decrease in intensity upon discontinuation of study drug despite other clear indications of relatedness)
- The event reappears or worsens when the study drug is re-administered

### **Unrelated to study drug (unlikely or unrelated)**

Based on medical judgment there is no reasonable possibility that the study drug caused the event; one or more of the following criteria apply:

- The event does not follow a reasonable temporal sequence from administration of study drug
- The event could be reasonably attributed to the known characteristics of the patient's clinical state, concurrent illness, environment or toxic factors, or other modes of therapy administered to the patient
- The event does not follow a known pattern of response to study drug
- The event does not disappear or decrease on cessation or reduction in dose of the study drug, and it does not reappear or worsen when the study drug is re-administered

## **10.1.2 Recording of Adverse Events**

It is the investigator's responsibility to assess whether each untoward event is a clinically significant worsening from baseline, thereby considered an AE. For all AEs, the severity, seriousness, and causality to study drug for each AE as outlined in [Section 10.1.1](#) will be assessed and recorded in the eCRF.

All serious and non-serious AEs are collected once the caregiver/patient has signed the ICF and until the post-treatment follow-up (Visit 10) or 28 days after the last dose of study drug.

Any AEs or SAEs that are unresolved at the patient's last AE assessment in the study are followed up by the investigator until resolution or stabilization up to the database lock and recorded in the eCRF. Albireo retains the right to request additional information for any patient with ongoing AE(s) or SAE(s) at the end of the study.

TEAEs are defined as any AE that occurs after randomization (Day 0). All AEs that occur in the Screening Period, i.e., after enrollment and prior to randomization, will be collected on the eCRF as non-treatment-emergent AEs.

If there is a clinically significant deterioration of a laboratory value/vital sign or other routine study assessment that is associated with a diagnosis, the clinical diagnosis will be reported as an AE and the associated signs and symptoms will be considered additional information unless the sign or symptom is more severe than expected given the diagnosis. For example, if an investigator diagnoses a study patient with hepatitis during the study period, hepatitis would be considered the AE and the concomitant signs and symptoms of abdominal pain, vomiting, and elevated ALT and AST would not be reported separately unless, in the opinion of the investigator, one of these signs or symptoms is more severe than expected and therefore a separate AE assessment is indicated.

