## 7 INVESTIGATIONAL PLAN

### 7.1 Overall Study Design and Plan

#### 7.1.1 Description

This is a double-blind, randomized, placebo-controlled, Phase 3 study to investigate the efficacy and safety of 40 µg/kg/day and 120 µg/kg/day of A4250 compared to placebo in children with PFIC (deficiencies of FIC1 or BSEP).

Study data will be periodically reviewed by an unblinded Data Safety and Monitoring Board (DSMB).

The study includes a 35- to 56-day Screening Period followed by a 24-week Treatment Period and a 4-week Follow-Up Period.

After completion of the Screening Period, eligible patients (20 per treatment group) will be randomized on Day 0 (Visit 3) in a 1:1:1 fashion to receive 40 µg/kg/day or 120 µg/kg/day of A4250, or a matching placebo.

Patients who complete the Treatment Period and Visit 9 (Day 168) in this study will be invited to participate in a 72-week open-label extension study (A4250-008, EudraCT Number 017-002325-38, subject to a separate study approval) in which all patients will receive active treatment. A patient who prematurely withdraws due to no improvement/intolerable symptoms, and has completed at least 12 weeks of the Treatment Period and End of Treatment (EOT) Visit, will also be offered the opportunity to enter Study A4250-008.

Visit windows applicable to each visit are presented in the schedule of assessments ([Table 1](#)). There will be up to 10 clinic visits during the study ([Figure 1](#)) and one scheduled telephone contact, as follows:

- Visit 1: Screening Period start. Patient is considered enrolled after signing the informed consent form (ICF) (Days -56 to -35)
- Visit 2: second Screening Visit (Days -28 to -7)
- Visit 3: Randomization Visit (Day 0)
- Telephone Contact 1: (Day 14)
- Visit 4: Clinic Visit (Day 28)
- Visit 5: Clinic Visit (Day 56)
- Visit 6: Clinic Visit (Day 84)
- Visit 7: Clinic Visit (Day 126)
- Visit 8: Clinic Visit (Day 154)
- Visit 9: Clinic Visit, EOT (Day 168)

- Visit 10: Follow-Up Visit, 28 days after last dose of study drug (Day 196). All patients continuing in Study A4250-008 will not have this Follow-up Visit.

Additional clinic visits may be required for patients who need direct site assistance, e.g., due to AE monitoring, to fulfil screening requirements, and/or for safety maintenance.

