#### **7.1.3.2 Treatment Period (Day 0 to Day 168)**

##### **Study Day 0/Clinic Visit 3 (Randomization)**

At the randomization visit, the following assessments will be conducted:

- Review inclusion/exclusion criteria ([Section 7.2](#))
- Review concomitant medications, medical and surgical history
- Physical examination, including voluntary photography ([Section 10.2.5](#))
- Skin examination ([Section 10.2.5](#))
- Vital signs ([Section 10.2.6](#))
- Albireo PRO/ObsRO eDiary review for compliance and entrance criteria requirement (see Inclusion Criteria 4, [Section 7.2.1](#))
- Clinical chemistry and hematology ([Section 10.2.1](#))
- s-BA ([Section 9.2.1](#))
- Autotaxin and p-C4 (samples will not be taken for patients  $\leq 10$  kg)
- Fat-soluble vitamin D
- Alfa-fetoprotein (AFP)
- Abdominal ultrasound ([Section 10.2.7](#))
- Fibroscan®, where available ([Section 9.2.7](#))
- Administer QoL (Pediatric Quality of Life Inventory [PedsQL]) questionnaire
- Patient/caregiver/clinician complete the patient global impression of symptoms (PGIS)
- Urine pregnancy test for girls who have reached menarche
- AE monitoring
- Study drug is dispensed and patients are instructed to administer daily from Day 1

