## 10 ASSESSMENT OF SAFETY

The timing and frequency of safety assessments are described in [Section 7.1.3](#) and in [Table 1](#) above.

The primary safety analysis for this study will include the incidence of total treatment-emergent adverse events (TEAE) and TEAEs categorized by causality, severity, and seriousness assessments made by the investigator by comparing study drug exposure to placebo.

Trends in safety will also be evaluated for the following assessments:

- Physical examinations
- Concomitant medications
- Vital signs
- Laboratory test results (including clinical chemistry, hematology, urinalysis, AFP, and fat-soluble vitamins A, D, and E)
- Abdominal ultrasound
- Discontinuations due to AEs

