#### **11.2.2.7 Evaluation of Safety Variables**

Safety data will be analyzed using descriptive statistics and summaries by treatment group of SAEs, AEs, vital signs, clinical laboratory tests (hematology, clinical chemistry and urinalysis), and concomitant medication. Analyses will be performed using the safety analysis set.

Summaries of AEs (coded according to the Medical Dictionary for Regulatory Activities [MedDRA] system organ class [SOC] and MedDRA preferred term) will include the following:

- Overview of the incidence of TEAEs (TEAEs, drug-related TEAEs, TEAEs leading to study discontinuation, and treatment-emergent SAEs)
- TEAEs by SOC and preferred term
- Intensity of TEAEs by SOC and preferred term
- Drug-related TEAEs by SOC and preferred term
- TEAEs leading to study discontinuation by SOC and preferred term
- Treatment-emergent SAEs by SOC and preferred term

Concomitant medication use during the Treatment Period will be summarized by Anatomical Therapeutic Chemical (ATC) class and World Health Organization (WHO) preferred name.

Summaries of vital signs will be presented. For each visit, the actual results and the change from baseline, and the number and percentage of patients with potentially clinically significant (PCS) values observed post-baseline will be presented.

Summaries of clinical safety laboratory data will be presented. For each visit, the actual result and the change from baseline, and the number and percentage of patients with PCS values observed post-baseline will be presented.

Data listings will be provided for each patient for all safety parameters.

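### The TEAE definition has no clause for worsening, so a screening-period AE that worsens on study drug may be left out of the TEAE tables

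*Protocol*

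**What the plan says.** Section 10.1.2 of the protocol starts AE collection at consent: "All serious and non-serious AEs are collected once the caregiver/patient has signed the ICF". It then fixes two classification rules. The first is "TEAEs are defined as any AE that occurs after randomization (Day 0"). The second is "All AEs that occur in the Screening Period, i.e., after enrollment and prior to randomization, will be collected on the eCRF as non-treatment-emergent AEs". The definition is the same in every protocol version in the file.

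Section 7.1.1 sets how long the screening rule operates: "The study includes a 35- to 56-day Screening Period followed by a 24-week Treatment Period and a 4-week Follow-Up Period". The Visit 3 procedures in Section 7.1.3.2 separate randomization on Day 0 from first dose: "Study drug is dispensed and patients are instructed to administer daily from Day 1".

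The main safety comparison rests on this classification. Section 10 says "The primary safety analysis for this study will include the incidence of total treatment-emergent adverse events (TEAE"), broken down by causality, severity and seriousness. The AE summaries itemised in Section 11.2.2.7 begin with "Overview of the incidence of TEAEs (TEAEs, drug-related TEAEs, TEAEs leading to study discontinuation, and treatment-emergent SAEs"), and the rest of that list is also confined to TEAEs or treatment-emergent SAEs.

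One sentence in Section 10.1.2 points the other way. It tells the investigator to "assess whether each untoward event is a clinically significant worsening from baseline, thereby considered an AE".

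**The concern.** A treatment-emergent definition should count events that begin after exposure and events that were already there and became worse after exposure. This definition speaks only of AEs that occur after randomization, and the sentence after it puts everything from screening on the other side of the line. A child who develops loose stools or vomiting during screening, still has them at Day 0, and becomes clearly worse on drug has an AE that is already classed as non-treatment-emergent.

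This matters more here than in many trials. Section 5.3.1 expects loose stools or diarrhea from the drug's mode of action. Exclusion criterion 4 removes only patients with chronic diarrhea that needed intravenous fluid or nutritional intervention. Milder gut symptoms can therefore be present before dosing and resemble a plausible drug effect. If sites handle their worsening differently, the inconsistency goes straight into small event counts.

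**Working it through.** The protocol gives no figure to reproduce. The check is a reading of the rules plus two small calculations.

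**Inputs**
- Screening length (Section 7.1.1): 35 to 56 days. 35/7 = 5 weeks and 56/7 = 8 weeks. AEs are collected throughout.
- TEAE clock (Section 10.1.2): randomization, Day 0.
- First dose (Section 7.1.3.2, Visit 3; Table 1, footnote l): Day 1.
- Planned arm size (Section 7.1.1): 20 patients.

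**Applying the rules to four kinds of event**
1. *Condition present at consent, worse on drug.* Section 10.1.1 counts only what occurs after enrollment as an AE, and Section 10.2.3 records earlier diagnoses as history. There is no screening AE record, so a deterioration after Day 0 can be entered as a new AE and counts as a TEAE.
2. *AE arising after first dose.* A TEAE on any reading.
3. *AE arising after randomization but before first dose.* A TEAE under the protocol, although no drug has been taken.
4. *AE arising between consent and Day 0, ongoing, worse after dosing.* Two readings are open:
   - The site keeps the existing record and follows it to resolution or stabilization, as Section 10.1.2 provides for unresolved events. The record carries the screening label and is not counted.
   - The site treats the worsening as a new AE under the worsening-from-baseline sentence. The new record falls after randomization and is counted.

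   No section chooses between these. Section 10.1.2 says what makes something an AE; it does not say that an AE already on file must be re-entered or reclassified when it worsens. Section 10.1.1.1 is permissive on deterioration. Nothing asks for the date or grade of a worsening.

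**Where a type 4 event would still appear**
- Laboratory values and vital signs: by-visit results, change from baseline and PCS counts (Section 11.2.2.7).
- Serious events: expedited reporting whatever the causality (Section 10.1.3).
- Discontinuations due to AEs: listed separately for evaluation in Section 10.
- Non-serious symptomatic worsening without discontinuation: certain only in the patient listings.

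**Size of one missed patient**
- Within one arm: 1/20 = 0.05, or 5 percentage points.
- Across both A4250 arms: 1/(20 + 20) = 1/40 = 0.025, or 2.5 percentage points.

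Both apply to an event category in which that patient has no other counted TEAE. Overall TEAE incidence does not move if the patient has any other TEAE during 24 weeks.

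**The case against.** The best defence is that the protocol's idea of an AE is itself one of worsening. On that view, a deterioration after Day 0 is a new AE that occurs after randomization, and the screening label attaches only to what happened in screening. Nothing forbids a new record. This stands as a mitigation: the loss is possible, not certain, and depends on site practice. It does not close the gap, because it allows a new record without requiring one.

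Three stronger readings are tempting, and the documents do not support them.
- A reader might infer that a screening event is locked as non-treatment-emergent even if it later becomes severe, serious or drug-related. The text does not say so, for the reason just given.
- A reader might infer that aggravation of the children's underlying liver and gut disease is hidden. Most such disease is present at consent and so carries no screening AE label. Liver chemistry is also summarised by visit, and Section 11.2.2.6 models ALT and total bilirubin by treatment group.
- A reader might want a count of lost patients. That needs the share of patients with an ongoing screening AE, the share of those who worsen, and the share whose sites do not re-enter the event. The protocol gives none of the three.

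It is also fair to say that the list in Section 11.2.2.7 is introduced as what the AE summaries will include, so it need not be exhaustive. The DSMB sees unblinded AE and laboratory data as well. The SAP, not available for this review, might refine the definition. But the protocol does not defer this one: it states the rule and the eCRF classification. A later analysis rule could not recover worsening dates and grades that sites were never asked to record.

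**Conclusion.** The point holds in a limited form. Section 10.1.2 leaves it undecided whether an AE that began between consent and Day 0 and worsened on drug is counted as treatment-emergent, and its literal classification leans toward leaving it out. The exposure is mainly to non-serious symptomatic events such as diarrhea and vomiting. How many patients are affected cannot be determined from the documents. The conditional size is 5 percentage points per patient for an event category in an arm of 20.

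The Day 0 anchor is a minor, separate flaw. It covers roughly a day, applies to all blinded arms alike, and adds pre-dose events to the count rather than losing any.

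The conclusion assumes planned arm sizes and rests on the protocol text at hand, which is the last of three parts; wording in the other parts could not be checked.

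**What to change.** Replace the definition in Section 10.1.2 with one on these lines: a TEAE is an AE that starts on or after the first dose of study drug, or that starts before the first dose and increases in severity or becomes serious after it. Limit the non-treatment-emergent label to AEs that start before the first dose and do not worsen in that sense afterwards. Instruct sites to enter each such worsening as a new eCRF record with its date and grade, so that all sites code it alike.

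The cost is one revised definition and a short eCRF completion instruction. The TEAE count may come out slightly higher. Dosing, visits and clinical management do not change.

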### **10.1.3 Recording and Reporting of Serious Adverse Events**

Every SAE (regardless of severity and causality) that occurs once the caregiver/patient has signed the ICF and until the post-treatment follow-up (Visit 10), and 28 days after the final dose of study drug, should immediately and not later than within 24 hours of knowledge of the event, be reported by the investigator or delegate in the SAE report form.

Report of a SAE must include at least the following information:

- Patient identification information (study number, site number, initials, and date of birth [as per local country requirements for data protection])
- The last study drug administration date
- The diagnosis of the event with the description (or a brief description of signs/symptoms/clinical course if the diagnosis is not available) and the date of onset
- The action used to treat the event (i.e., treatment medications, temporary discontinuation)
- The reason(s) for considering the event serious
- The relationship of the event to the study drug or to the study procedure (e.g., the investigator's assessment of causality)
- A brief narrative of the SAE

Follow-up reports including all new information obtained of the subsequent course of the SAE must be prepared and the information collected in the SAE submitted to [REDACTED] (Pharmacovigilance and Safety Services Department) by e-mail within 24 hours of knowledge of the event.

The pharmacovigilance manager (PVM) may contact the investigator to obtain further information on a reported SAE. The investigator/investigative staff must respond to any request for follow-up information or answers to questions regarding the SAE within the same timelines as for initial reports.

The PVM reports the occurrence of the SAE and follow-up to the Albireo medical monitor for medical assessment of the case.

Should an outcome of death occur within the study period or within 28 days after the last administration of study drug, an SAE form should be completed including the main and contributory causes of death.

All SAE reports must be e-mailed to the following e-mail address within **24 hours**:

[REDACTED]

If email is unavailable, SAEs may be transmitted via fax to the following number:

[REDACTED]

In a study-related medical emergency situation, when the assigned medical monitors for the study cannot be reached by a caller, an on call physician can be reached 24 hours per day, 7 days per week, via the [REDACTED] call center. The following number is a chargeable telephone number allowing a global reach from both landlines and mobile phones and the internet page indicated below contains a list of country-specific toll-free telephone numbers that is provided. It should be noted that not all countries globally have access to toll-free numbers as indicated on the “24/7 Medical Help desk” index. Countries without toll-free numbers need to dial the chargeable number as indicated below. Furthermore, toll-free numbers might not be available from mobile phones.

[REDACTED]

#### **10.1.4 Reporting of Suspected Unexpected Serious Adverse Reactions**

Suspected unexpected serious adverse reaction (SUSAR) is an SAE that occurs in a patient, the nature or severity of which is not expected per the applicable product information (e.g., the IB for an unauthorized investigational product or summary of product characteristics for an authorized product).

Reporting and tracking of SUSARs will be in accordance to all applicable competent authority regulations. The Ethics Committee and all investigators involved in this study will be informed according to national and international requirements.

### **10.2 Laboratory Values/Vital Signs/Physical Examinations and Other Safety Assessments**

#### **10.2.1 Laboratory Assessments**

Samples will be collected for clinical chemistry, hematology, and urinalysis testing at the time points specified in [Table 1](#). The parameters assessed are presented in [Table 3](#).

Blood for AFP will be drawn at Visits 3 and 9 and for fat-soluble vitamins at Visits 2, 3, and 9.

A serum pregnancy test will be performed at Visit 1 and Visit 9 if the patient is entering the A4250-008 study. A urine pregnancy test will be collected at all other visits for girls who have reached menarche. If a urine pregnancy test is positive, a serum pregnancy test should be performed to confirm the pregnancy. Study drug administration will be held pending the confirmatory results. If the serum pregnancy test is negative, the patient can resume dosing. If the serum pregnancy test is positive, the patient should be discontinued (see [Section 10.2.9](#)).

All samples will be processed and transported to a laboratory per instructions in the laboratory manual.

The observed values will be recorded and assessed as “normal” or “abnormal not clinically significant” or “abnormal clinically significant”.

Additional safety blood samples may be needed due to follow-up of an abnormal value or analysis failure. The blood samples collected for safety laboratory analysis will be destroyed after the analyses have been completed.

